## List of abbreviations:

LBBB = left bundle branch block	CAD = coronary artery disease
ECG = electrocardiogram	LV = left ventricle/left ventricular
PVP = predominant ventricular pacing	CRT = cardiac resynchronization therapy
PM = pacemaker	BP = blood pressure
AI = artificial intelligence	HBP = his bundle pacing
NPR = Norwegian Patient Registry	EF = ejection fraction
RBBB = right bundle branch block	MACCE = major adverse cardiovascular and cerebral

## 1 Background

This study is a cardiovascular study, especially relevant for the elderly population, aiming to identify individuals with left bundle branch block (LBBB) who are at high risk for developing heart failure and increased risk for cardiovascular morbidity and mortality. In patients with LBBB, cardiac resynchronization therapy (CRT) has the ability to reverse heart failure and reduce morbidity and mortality with high effectivity (1,2). However, CRT is an invasive procedure with inherent short- and long-term complications and a substantial rate of non-responders. Improved patient selection will be needed for better outcome of an already well-established therapy. Low-risk patients with stable conditions need to be identified to be assigned to an individually adjusted follow-up. Thus, careful selection of potential CRT responders at the appropriate time-point is crucial for optimal patient treatment. For the time being, the identification of high and low-risk patients is the most important step before new randomized controlled trials for CRT treatment should be conducted.

LBBB is relatively common in the cardiovascular patient population and is known to be associated with increased risk for the development of congestive heart failure and risk for mortality (3). However, asymptomatic individuals with structurally normal hearts can also have LBBB. Prognosis of LBBB in population-based studies is highly dependent on age and comorbidity (4-8). Both, population based, and clinical studies demonstrate that electrocardiogram (ECG) criteria and clinical findings alone are not specific enough to develop risk assessment algorithms for cardiovascular morbidity and mortality in the LBBB population, thus the number of publications of the natural history of LBBB has rapidly decreased since 2005. However, recent experimental and clinical studies using modern echocardiographic tools as well as computer models for regional deformation imaging of the heart have given new insights into the pathophysiology of LBBB and the interplay between delayed electrical activation of parts of the left

ventricle (LV), and the presence of myocardial scars. Only recently the equal effect of loading and QRS on dyssynchrony has been better understood. Artificial intelligence (AI) can use information from strain-curve analysis together with other echocardiographic and clinical information to identify patients at risk and treatment responders (9). Based on these new insights, this study aims to investigate the potential of new echocardiographic and AI methods, in combination with clinical information and afterload assessment (ventricular dimensions and geometry combined with blood pressure (BP)). These easily obtainable parameters might hopefully become a new cornerstone for development of risk-assessment algorithms as a basis for individual treatment recommendation.

The recent development of ultrasound-based quantification of dyssynchrony seems to be a promising tool for individual risk-stratification(10-12). Patient at risk might undergo timely CRT treatment before heart failure is fully established or the mortality risk increases. To the best of our knowledge this will be the first longitudinal study on echocardiographic functional markers for dyssynchrony in the general LBBB population. Additionally, AI algorithms will hopefully improve identification of patients at risk for heart failure development. The aim is to identify the time-point when a stable state with LBBB turns into deteriorating heart failure, which is probably the best time-point when specific treatment needs to be applied and heart failure can be reversed.

This study will include prospectively clinical patients from the cardiological outpatients' clinics, and the cardiology wards in University Hospital of North Norway Tromsø and Harstad, Akershus University Hospital, Lørenskog, Oslo University Hospital, Rikshospitalet, Haukeland University Hospital, Bergen and Nordlands Hospital, Bodø. Furthermore, we intend to use retrospectively collected data of population-based study from the Katholieke Universiteit (KU) Leuven, Belgium and invite participants with LBBB or predominant ventricular pacing (PVP) from the Tromsø 7 study for the prospective study. The study is furthermore open to include retrospectively datasets where subjects with LBBB or PVP can be identified and echocardiographies are taken (e.g. St. Olav Hospital, Trondheim). Prospectively included patients will be followed by a repeated echocardiography study after one year and access to patient registries through 5 years (eventually up to 15 years). All studies abroad will follow their own study protocol and follow-up.

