### 1.7 Clinical significance:

LBBB is highly prevalent among patients with chronic heart failure (25%). Morbidity and mortality are high among patients with LBBB, but ECG detected LBBB has not been shown to be a sufficiently accurate predictor of outcome. Early medical treatment or CRT for carefully selected individuals might help to lower morbidity and mortality among individuals with LBBB or PVP. However, criteria for an optimal time-point and patient characteristics for CRT responders are still missing.

In conclusion, the study aims to identify new predictors for the appropriate time point for initiating specific treatment, as well as specific patient characteristics for treatment response based on AI and novel echocardiographic measures. Risk- algorithms for heart failure and increased mortality are

urgently needed in this large group of cardiological patients (25% of heart failure patients). Studies on patients with CRT have demonstrated high specificity of echocardiographic parameters when heart failure is established. Other newer parameters like “septal and lateral work” and as well as integration of all accessible features by AI have been recently introduced and shown to provide a powerful tool for differentiating degrees of dyssynchrony in patients with LBBB. This study aims to contribute to a more specific patient selection for specific heart failure treatment, when LBBB or PVP is present. Patients with His bundle pacing (HBP) might provide synchronous pacing and are also included as a special control-group for patients with permanent ventricular pacing.

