### **2.2 Secondary hypotheses**

1. Patients with high afterload have typical dyssynchrony patterns with earlier deterioration of cardiac function over time.
2. Repetition of echocardiographic assessment and clinical parameters increases accuracies of outcome-prediction.
3. Predictors for major adverse cardiovascular and cerebrovascular events (MACCE) indicate also CRT- or medical treatment- response. These factors might be useful indicators for risk reduction through treatment of carefully selected patient-groups
4. Patients showing ability to increase or sustain myocardial work during a stress test with no classic pattern of dyssynchrony have a good long-term prognosis.
5. HBP can prevent development of heart failure compared to usual ventricular pacing.

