## 3 Project arrangements, method selection and analyses

### 3.1 Patients

This is a longitudinal prospective cohort-study intending to include at least 1000 patients with LBBB from University Hospital of North Norway Tromsø and Harstad, Akershus University Hospital, Lørenskog, Oslo University Hospital, Rikshospitalet, Haukeland University Hospital, Bergen and Nordlands Hospital, Bodø, over a 2-year inclusion period.

Information about present and previous diseases, medication, surgical- or invasive treatment, PM, ICD or CRT implantation, clinical examination and present and previous echocardiographic imaging and blood samples (Hb, Thrombocytes, CRP, Kreatinine, eGFR, Urate, HbA1C, Cholesterol, ProBNP, Troponins, ALAT and Ferritin) will be accessed by the patient's journal.

All prospective study participants will answer one customized and two standardized (EQ5D and HeartQoL) questionnaires. They will undergo general clinical investigation comprising height and weight measurements, baseline ECG, blood samples when not found in the patient's journal, standardized BP measurements and echocardiography with a 3 minutes- hand-grip test at baseline and in a 18 month follow-up study.

Clinical outcome data including death and hospital admissions due to heart failure and CRT implantation will be assessed after 3 and 5 years (eventually after 10 and 15 years) by linkage to data from the patient's clinical records through access to Norwegian Patient Registry (Norsk pasientregister (NPR)), Norwegian Causes of Death Registry (Dødsårsaksregisteret) and Norwegian Cardiovascular Disease Registry (Hjerte- og karregisteret).

St Olavs Hospital, Trondheim, might provide retrospective patient data with echocardiography loops, where outcome-data will be extracted from the same registries.

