### 3.11 Statistics

Patients with deteriorating myocardial function will be identified by increasing proBNP by more than 10%, increasing NYHA class, increasing diastolic volume by more than 10% and/or decreasing EF by more than 5%. ANOVA will be used to compare parameters between patients with deteriorating myocardial function and those with unchanged clinical condition after one year. ROC curve analysis will serve to find the ideal cut-off values for continuous variables and assessing sensitivity and specificity of the tests. Univariate and multivariate logistic regression tests will be performed in order to identify the most powerful parameters predicting development of heart-failure with hospital admissions as primary outcome and predicting death (or transplantation) as secondary outcome.

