### 3.12 Data management

Data from patient's visit and patient's journal will be stored as de-identified data in an a password secured internet-based database (Viedoc). Viedoc is approved by The Norwegian Data Protection Authority for use in scientific studies. Echocardiographic data will be stored as de-identified DICOM files including locally performed measurements, labeled by the patient's study ID, all ECGs will be taken in digitalized format and be stored as de-identified image files as well as DICOM files. All de-identified files will be locally stored at a dedicated server. Key files coupling personal patient information to ID's will be stored locally on a server with restricted access. All de-identified ECGs, echocardiography-studies and key-files will be centrally collected at University Hospital of North Norway, Tromsø, latest after end of the second patient's visit. Echocardiographic data will be analyzed in the core-lab at University Hospital of North Norway, Tromsø. Readers of the strain-data will be blinded for the outcome-data. Other researchers assess outcome-data from NPR and The Norwegian Cause of Death Registry will be added to the database. The de-identified dataset and DICOM images from echocardiography and ECG will also be transferred to NTNU Trondheim for automated reading of the echocardiographic imaging and AI purposes.

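### Secondary hypothesis 1 claims earlier deterioration with high afterload, but a single yes/no repeat assessment shows only whether it is more frequent by that visit, and registry events are analysed without their timing

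*Protocol*

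**What the plan says.** Timing language appears in three places in the Protocol. Section 1 (Background) states: "The aim is to identify the time-point when a stable state with LBBB turns into deteriorating heart failure". Section 1.7 says that "the study aims to identify new predictors for the appropriate time point for initiating specific treatment". Section 2.2, secondary hypothesis 1, reads: "Patients with high afterload have typical dyssynchrony patterns with earlier deterioration of cardiac function over time".

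The schedule has two assessments. Section 1 says: "Prospectively included patients will be followed by a repeated echocardiography study after one year and access to patient registries through 5 years". Section 3.1 instead describes "echocardiography with a 3 minutes- hand-grip test at baseline and in a 18 month follow-up study". Section 3.12 fits two visits, since the files are to be collected centrally "latest after end of the second patient's visit".

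Section 3.4 sets the primary outcome as change in markers of myocardial function, reduced to deterioration or non-deterioration.

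For analysis, section 3.11 says: "ANOVA will be used to compare parameters between patients with deteriorating myocardial function and those with unchanged clinical condition after one year". It adds ROC curves, and logistic regression for heart failure with hospital admission and for death or transplantation. Section 3.1 has registry outcomes assessed after 3 and 5 years. Section 3.10 refers to hazard ratios for hospital admission, comparing patients with and without deterioration of left ventricular function.

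**The concern.** A hypothesis that one group deteriorates earlier is a statement about when onset happens. Two assessments and a yes/no outcome record only whether onset has happened by the second one. A higher proportion in the high-afterload group would support the statement that deterioration is more frequent by that visit. Without a further assumption it would not support the word in the hypothesis.

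The registry outcomes raise a related problem. They are the one part of the study where event timing should be available over several years, and section 3.11 assigns them to a method that ignores it. Section 3.10, by contrast, is written as if a time-to-event analysis were intended.

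What is at stake is how one secondary hypothesis can be interpreted, and how efficiently the admission and mortality data are used. The Background links the turning point to when treatment should be applied, so unsupported timing language could carry weight with readers.

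**Working it through.** The protocol gives no figure on this point to reproduce. The check sets the schedule and methods against the hypothesis and adds small illustrations.

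**1. What each patient contributes.** Inputs: two scheduled assessments (sections 1, 3.1, 3.12) and a binary outcome (section 3.4). With the repeat visit at time T, the record is whether onset lies in (0, T]. T is the same for everyone: 12 months in section 1 or 18 months in section 3.1.

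**2. How loosely onset is dated.** Assume, for illustration, that onset is uniform over the gap. The standard deviation of the unknown onset time is T/√12.
- T = 12: 12/3.464 = 3.5 months.
- T = 18: 18/3.464 = 5.2 months.

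**3. Frequency and timing can come apart.** Take T = 12. The proportions are two of the scenarios in section 3.10; the onset patterns are invented.
- Equal proportions, different timing: 10% deteriorate in each group, with onset uniform over months 0–6 under high afterload (mean 3) and over months 6–12 otherwise (mean 9). At the visit both groups show 10%, so the odds ratio is 1 and a real timing difference is missed.
- Higher proportion, later timing: 20% under high afterload with onset in months 6–12, and 10% otherwise with onset in months 0–6. The odds ratio is (0.20/0.80)/(0.10/0.90) = 0.250/0.111 = 2.25, although those who deteriorate under high afterload do so later.

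**4. What an assumption would buy.** Under proportional hazards, one inspection time identifies the hazard ratio: HR = ln(1 − p₁)/ln(1 − p₀). With p₁ = 0.20 and p₀ = 0.10, HR = (−0.2231)/(−0.1054) = 2.12. On that assumption, onset is stochastically earlier in the high-afterload group. The protocol does not state the assumption, and a single inspection time cannot check it.

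**5. Methods set against the hypothesis.** ANOVA compares parameters between deteriorated and unchanged patients. ROC curves choose cut-offs. Logistic regression models whether an event occurred. None of these uses time of onset.

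**6. Registry events.** In a logistic model read at 3 years, an admission in the first month and one in the last month count alike. A patient who dies without an admission counts as not admitted, unless handled separately. The hazard ratios in section 3.10 have no corresponding model in section 3.11.

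**The case against.** Several points on the other side have force.

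- *The Background sentence is not an objective.* This stands. No numbered objective in sections 2.3 and 2.4 asks for deterioration to be dated. Secondary objective 1, the counterpart of the hypothesis, concerns how strain patterns depend on afterload and geometry, which baseline data can address. The word time-point can also mean disease stage. On that reading, predicting who will have deteriorated by follow-up serves the aim.
- *One inspection time is informative.* This also stands, as step 4 shows. A reader might infer that the design cannot say anything about earlier deterioration and that the timing aim fails outright. The documents do not support that: the data need an added assumption.
- *The plan is not wholly time-free.* Correct. Section 3.10 mentions hazard ratios. However, they concern admission, with deterioration as the grouping factor, so they do not date the functional change.
- *Other echocardiograms exist.* Section 3.1 accesses earlier ones, but section 3.6 specifies their retrospective reading only for patients who already have CRT. They were not taken on a study schedule.
- *Models belong in the analysis plan.* This is partly right. A separate plan could add detail, but it cannot add echo visits, and section 3.11 itself names the method for registry events.

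A reader might also multiply the 5% to 30% scenarios by the planned 1000 patients to count undated cases. Section 3.10 calls the true rate unknown, and such counts measure neither bias nor lost power. Nor does the protocol say that a higher proportion will be reported as earlier deterioration.

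**Conclusion.** The point holds as a mismatch between the wording of one secondary hypothesis and what the two assessments can show, together with a poor choice of method for registry events. With one repeat assessment scored yes or no, the study can estimate whether high afterload goes with more frequent deterioration by that visit. Reading this as earlier deterioration needs proportional hazards or a similar assumption, which the protocol does not state and its two visits cannot test. The onset standard deviations of 3.5 and 5.2 months rest on an assumed uniform onset and are illustrative.

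For registry outcomes, logistic regression discards timing over 3 to 5 years and does not match the hazard ratios in section 3.10. This assumes that the registry linkage yields event dates, which the protocol does not say outright but which hazard ratios would require.

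The prediction objectives are not undermined. The repeat visit is at one year in sections 1, 2.4, 3.11 and 4 but at 18 months in section 3.1. Those passages contradict each other and must be reconciled, because the visit time defines the outcome.

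**What to change.** (a) Reword secondary hypothesis 1 so that high afterload is tied to a higher probability of deteriorated function by the repeat visit, and bring the Background sentence into line. In the same edit, reconcile the one-year and 18-month visit times, so that 'by the repeat visit' has one meaning throughout.

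(b) In section 3.11, replace logistic regression for registry heart-failure admission and for death with Cox models of time from baseline to first event, with baseline afterload among the predictors. State how death is handled in the admission model, for example by censoring at death and reporting a cause-specific hazard. Name the admission type once, since section 3.10 refers to cardiovascular and section 3.11 to heart-failure admission. Say plainly that these models describe the timing of clinical events, which may come later than the change in ventricular function and do not date it.

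A mixed model of ejection fraction and volume using earlier clinical echocardiograms is optional. It should be labelled descriptive, because those studies were not taken on a study schedule.

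The cost is wording plus slightly more analysis work on data already planned. No extra visits or data sources are needed.

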## 1.1 Epidemiology and etiology

LBBB occurs frequently in various cardiac diseases of differing etiology. The presence of LBBB has been reported to adversely affect prognosis even in individuals who have no symptoms or known cardiovascular disorders and LBBB has been an incidental finding on ECG. Thus, individuals with LBBB are reported to have increased risk of death or heart failure (13,14).

LBBB almost never occurs before 35 years of age, suggesting it could be an acquired condition (15). In population-based studies the prevalence of LBBB ranges between 0.1 and 0.8% (3,7,16). The prevalence of LBBB strongly correlates with age with an average age at LBBB diagnosis being  $70 \pm 10$  years in men and  $68 \pm 11$  years in women (17). Proportion of those with LBBB increases progressively from <1% at age of 50 to 6% by 80 years (17,18). Factors found to be associated with its development included arterial hypertension, coronary artery disease (CAD), valvular heart disease, cardiomyopathies, myocarditis which all are states with known myocardial macro- or micro fibrosis (15,17). Recent human and animal studies suggest gene expression of connexin 40 and 43 to be involved in the development of LBBB and cardiomyopathy (19,20).

## 1.2 Prognosis

To date there is no consensus on LBBB-related prognosis as study results are clearly influenced by study design, population size, selection criteria and age (21). In 1979 the Framingham Study (4209 subjects, 55 with LBBB) (6) showed a clear association between LBBB and main cardiovascular diseases, such as hypertension, cardiac enlargement and CAD. Coincident with or subsequent to the detection of LBBB, 48% of these individuals developed congestive heart failure. Within 10 years from LBBB detection, cardiovascular mortality was 50% and at 18 years follow-up only 11% of subjects with LBBB remained free of detectable cardiovascular abnormalities. Several studies showed that once a LBBB is established, the prognosis worsens with age, established CAD or congestive heart failure (3,5,7,22,23). In patients with acute myocardial infarctions with LBBB, 30 days mortality, in-hospital death and 1 year's mortality were reported to be substantially increased (3,22,24,25).

### 1.3 Pathophysiology

In addition to patients with “spontaneous” LBBB, pacemaker (PM)- patients with PVP often develop conduction disturbances resembling an electro-mechanical activation pattern of a LBBB. LBBB or PVP result in regionally delayed electrical activation with comparable hemodynamic effect (26).

Individuals with LBBB or PVP develop delayed electrical activation of the lateral wall of the LV (27). During the septal contraction, the intraventricular pressure rise is low. The delayed lateral wall contraction leads to stretching of the septum during the ejection phase, which does not contribute to further pressure generation or stroke volume. Consequently, the regional work load of the septum is reduced, while the work load of the lateral wall increases due to initial pre-stretch. Perfusion imaging shows relative septal hypoperfusion (28,29). Animal-models have shown an unfavorable effect on LV remodeling including LV dilatation, asymmetric hypertrophy and decreased pump function (29), altered cellular Ca++ transport and a pro-arrhythmic state (15). Deformation of the mitral valve apparatus with annular dilatation and dyssynchronous papillary muscle contraction lead to development and progression of functional mitral regurgitation (30,31) which aggravates heart failure development. However, the presence of LBBB alone seems not to cause ventricular dysfunction and heart failure. First, when the LV starts to become dyssynchronous and inefficient (32,33) a vicious cycle starts with progressive LV failure and progression of the conduction abnormality as well (34,35).

Recent computational, experimental and clinical studies showed the deleterious role of increased afterload, causing higher wall stress, when either the ventricle is dilated, or intraventricular pressure is high. These conditions seem to influence the degree of dyssynchrony and seem to contribute substantially to reduced cardiac performance when delayed electrical activation is present (36-38). These recent publications seem to be the missing link to be able to predict the prognosis on individual basis.

